8.2. Discontinuation from the Study

Patients will be discontinued from the study in the following circumstances:

- participation in the study needs to be stopped for medical, safety, regulatory, or other reasons consistent with applicable laws, regulations, and good clinical practice (GCP)
- the investigator decides that the patient should be discontinued from the study
- the patient requests to be discontinued from the study

Patients who discontinue from the study early will have end-of-study procedures performed as shown in the Schedule of Activities (Section 2).

8.3. Lost to Follow-Up

A patient will be considered lost to follow-up if he or she repeatedly fails to return for scheduled visits and is unable to be contacted by the study site. Study site personnel are expected to make diligent attempts to contact patients who fail to return for a scheduled visit or who the site is otherwise unable to follow-up.

Study site personnel, or an independent third party, will attempt to collect the survival status for all enrolled patients who are lost to follow-up, within legal and ethical boundaries. Public sources may be searched for survival status information. If the patient's survival status is determined, the survival status will be documented, and the patient will not be considered lost to follow-up.

Lilly personnel will not be involved in any attempts to collect survival status information.

9. Study Assessments and Procedures

Section 2 provides the Schedule of Activities for this study.

Appendix 3 provides a list of the laboratory tests that will be performed for this study.

Appendix 4 provides the schedule for collection of samples in this study.

Unless otherwise stated in the following subsections, all samples collected for specified laboratory tests will be destroyed within 60 days after receipt of confirmed test results. Certain samples may be retained for a longer period, if necessary, to comply with applicable laws, regulations, or laboratory certification standards.

9.1. Efficacy Assessments

Tumor assessments will be performed for each patient at the times shown in the Schedule of Activities (Section 2).

Computed tomography (CT) scans, including spiral CT, are the preferred methods of measurement (CT scan thickness recommended to be ≤ 5 mm); however, magnetic resonance imaging (MRI) is also acceptable in certain situations, such as when body scans are indicated or if there is a concern about radiation exposure associated with CT. Intravenous and oral contrast is required unless medically contraindicated.

The CT portion of a positron emission tomography (PET)-CT scan may be used as a method of response assessment if the CT is of identical diagnostic quality to a diagnostic CT (with IV and oral contrast). A PET scan alone or as part of a PET-CT may be performed for additional analyses but cannot be used to assess response according to RECIST v.1.1 (Eisenhauer et al. 2009).

Radiologic scans of the thorax and abdomen are required. A baseline intracranial evaluation with CT or MRI should be conducted. Scans of the pelvis or bone scans should be performed if clinically indicated. Copies of the scans may be requested by the sponsor for central review.

See Section 10.3.1 for definitions of the efficacy endpoints.

9.1.1. Appropriateness of Assessments

The measures used to assess safety and efficacy in this study are consistent with those used in most conventional oncology trials.

9.2. Adverse Events

The investigator will use Common Terminology Criteria for Adverse Events Version 4.0 (NCI 2009) to assign AE terms and severity grades.

Investigators are responsible for:

- monitoring the safety of patients in this study and for alerting Lilly or its designee to any event that seems unusual, even if this event may be considered an unanticipated benefit to the patient
- the appropriate medical care of patients during the study
- documenting their review of each laboratory safety report
- following, through an appropriate health care option, AEs that are serious or otherwise medically important, considered related to study treatment or the study, or that caused the patient to discontinue LY2606368 before completing the study. The patient should be followed until the event resolves, stabilizes with appropriate diagnostic evaluation, or is reasonably explained. Frequency of follow-up evaluation is left to the discretion of the investigator.

Lack of drug effect is not an AE in clinical studies, because the purpose of the clinical study is to establish treatment effect.

After the ICF is signed, study site personnel will record via case report form (CRF)/electronic data entry/designated data transmission methods the occurrence and nature of each patient's preexisting conditions, including clinically significant signs and symptoms of the disease under treatment in the study. In addition, study site personnel will record via CRF/electronic data entry/designated data transmission methods any change in the preexisting conditions and any new conditions as AEs. Investigators should record their assessment of the potential relatedness of each AE to study procedure or LY2606368 via CRF/electronic data entry/designated data transmission methods.

The investigator will interpret and document whether or not an AE has a reasonable possibility of being related to study treatment or a study procedure, taking into account the disease, concomitant treatments, or pathologies. A "reasonable possibility" means that there is a cause and effect relationship between the study treatment and/or study procedure and the AE.

Planned surgeries and nonsurgical interventions should not be reported as AEs unless the underlying medical condition has worsened during the course of the study.

Study site personnel must report any dose modifications or treatment discontinuations that result from AEs to Lilly or its designee via CRF/electronic data entry/designated data transmission methods, clarifying, if possible, the circumstances leading to the dose modification or discontinuation of treatment.

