Relative day within a cycle		Period begins the day after stopping of study treatment and lasts approximately 30 days	Period begins 1 day after short-term follow-up period is completed and continues until death, study withdrawal, or the patient is lost to follow-up	
Procedure Category	Procedure			Comments
Physical Examination	Physical examination (including weight)	X		
	Vital signs	X		Includes blood pressure, pulse, and temperature.
	ECOG performance status	X		
Tumor Assessment	Radiologic imaging according to RECIST 1.1	X		The same method of imaging (CT scan, spiral CT, etc.) used at baseline should be used for each subsequent assessment. Not required if progressive disease is documented while on treatment or if there are clear signs of clinical progression.
	Tumor measurement (palpable or visible)	X		Performed at the same time as radiologic imaging.
Adverse Events Collection/CTCAE Grading		X	X	After Visit 801, only study treatment-related serious events are reported.
Concomitant Medication Notation		X		
Lab/Diagnostic Tests	Hematology	X		
	Chemistry	X		
	ECG	X		
	Exploratory blood sample for biomarkers	X		
	Plasma biomarker sample	X		
	Optional posttreatment biopsy		X	
Health Outcome Measure	Lung Cancer Symptom Scale	X		The LCSS will need to be administered prior to extensive interaction with site personnel.
Follow-Up	Survival Assessment		X	Approximately every 60 (±14) days (telephone assessment is acceptable).

Abbreviations: CT = computed tomography; CTCAE = Common Terminology Criteria for Adverse Events (NCI 2009); ECOG = Eastern Cooperative Oncology Group (Oken et al. 1982); LCSS = Lung Cancer Symptom Scale; RECIST 1.1 = Response Criteria In Solid Tumors Version 1.1 (Eisenhauer et al. 2009).

Table JTJH.2.4. Continued Access Schedule of Activities

	Study Treatment	Follow-Up ^a	
Visit	501-5XX	901	
Procedure ^b			Comments
AE collection	X	X	
Administer LY2606368	X		IV over approximately 60 (+10) minutes once every 14 days.

Abbreviations: AE = adverse event; IV = intravenously.

- a Continued access follow-up begins 1 day after the patient and the investigator agree that the patient will no longer continue treatment in the continued access period and lasts approximately 30 days. No follow-up procedures will be performed for a patient who withdraws informed consent unless he or she has explicitly provided permission and consent.
- b Efficacy assessments will be done at the investigator's discretion based on the standard of care.

3. Introduction

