9.2.1. Serious Adverse Events

An SAE is any AE from this study that results in one of the following outcomes:

- death
- initial or prolonged inpatient hospitalization
- a life-threatening experience (that is, immediate risk of dying)
- persistent or significant disability/incapacity

- congenital anomaly/birth defect
- considered significant by the investigator for any other reason: important medical events that may not result in death, be life-threatening, or require hospitalization may be considered serious, based upon appropriate medical judgment.

Although all AEs after signing the ICF are recorded in the CRF/electronic data entry/designated data transmission methods, SAE reporting begins after the patient has signed the ICF and has received LY2606368. However, if an SAE occurs after signing the ICF, but prior to receiving LY2606368, it needs to be reported ONLY if it is considered reasonably possibly related to study procedure.

Study site personnel must notify Lilly or its designee of any SAE within 24 hours of investigator awareness of the event via a Lilly-approved method. If alerts are issued via telephone, they are to be immediately followed with official notification on study-specific SAE forms. This 24-hour notification requirement refers to the initial SAE information and all follow-up SAE information.

Pregnancy (during maternal or paternal exposure to LY2606368) does not meet the definition of an AE but should be reported. However, to fulfill regulatory requirements, any pregnancy should be reported following the SAE process to collect data on the outcome for both mother and fetus.

Investigators are not obligated to actively seek AEs or SAEs in patients once they have discontinued and/or completed the study (the patient summary CRF has been completed). However, if the investigator learns of any SAE, including a death, at any time after a patient has been discharged from the study, and he/she considers the event reasonably possibly related to the study treatment or study participation, the investigator must promptly notify Lilly.

Planned hospitalizations or procedures for preexisting conditions that were recorded in the patient's medical history at the time of enrollment should not be considered SAEs. Hospitalization or prolongation of hospitalization without a precipitating clinical AE (for example, for the administration of study treatment or other protocol-required procedure) should not be considered an SAE.

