Serious adverse events, including death, caused by disease progression should not be reported unless the investigator deems them to be possibly related to LY2606368.

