9.2.2. Suspected Unexpected Serious Adverse Reactions

Suspected unexpected serious adverse reactions (SUSARs) are serious events that are not listed in the IB and that the investigator identifies as related to study treatment or study procedure. United States 21 CFR 312.32 and European Union Clinical Trial Directive 2001/20/EC and the associated detailed guidances or national regulatory requirements in participating countries require the reporting of SUSARs. Lilly has procedures that will be followed for the recording and expedited reporting of SUSARs that are consistent with global regulations and associated detailed guidances.

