5.13.2. Adverse Events

All patients who receive at least one dose of study treatment will be evaluated for safety and toxicity. Adverse event terms and severity grades will be assigned by the investigator using CTCAE v4.0X. In addition, AE verbatim text will also be mapped by the sponsor or designee to corresponding terminology within the Medical Dictionary for Regulatory Activities (MedDRA). Adverse events will be reported using a unified CTCAE/MedDRA reporting process:

- The CTCAE v4.0 term reported by the investigator will be mapped to the MedDRA preferred term (PT) and system organ class (SOC) of the corresponding MedDRA lowest level term (LLT), unless the reported CTCAE term is ‘Other – specify’
- If the reported CTCAE term is ‘Other – specify’ the MedDRA LLT, PT and SOC mapped from the verbatim AE term will be used
- All listings and summaries will use the MedDRA LLT and the MedDRA PT resulting from this process.

A treatment-emergent adverse event (TEAE) is defined as an event that first occurred or worsened in CTCAE grade after the first dose of study treatment. The MedDRA LLT will be used in the treatment-emergent computation.

All observed AEs will be graded using CTCAE version 4.0. Adverse events, deaths and serious adverse events (SAEs) will be listed and summarized. Summaries for patients on therapy will include:

- Summary of all pre-existing conditions and AEs
- Summary of all TEAEs
- Summary of TEAEs possibly related to study treatment
- Summary of all TEAEs by maximum CTCAE grade
- Summary of TEAEs possibly related to study treatment by maximum CTCAE grade
- Summary of deaths on treatment or post-study treatment deaths possibly related to study treatment.

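### Protocol Section 9.2 defines a possible drug relationship as an established one, and this is the only definition behind the rules that depend on relatedness

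*Protocol*

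**What the plan says.** Protocol Section 9.2 tells the investigator to record the potential relatedness of each AE and to document "whether or not an AE has a reasonable possibility of being related to study treatment or a study procedure". The next sentence defines the key phrase: a reasonable possibility "means that there is a cause and effect relationship between the study treatment and/or study procedure and the AE".

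Several rules then depend on that judgement:

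- **Late events (Protocol Table JTJH.2.3):** "After Visit 801, only study treatment-related serious events are reported".
- **SAEs before first dose (Protocol 9.2.1):** these are reported only if considered reasonably possibly related to a study procedure.
- **SAEs after discharge (Protocol 9.2.1):** for an SAE learned of after the patient has left the study, the duty to report applies if "he/she considers the event reasonably possibly related to the study treatment or study participation, the investigator must promptly notify Lilly".
- **Progression (Protocol 9.2.1):** SAEs, including deaths, "caused by disease progression should not be reported unless the investigator deems them to be possibly related to LY2606368".
- **SUSARs (Protocol 9.2.2):** these are unlisted serious events "that the investigator identifies as related to study treatment or study procedure".
- **Tables (SAP 5.13.2):** there are separate summaries of TEAEs possibly related to treatment, and one line reads "Summary of deaths on treatment or post-study treatment deaths possibly related to study treatment".

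**The concern.** The definition contradicts the term that it defines. A reasonable possibility is a statement of uncertainty, but the definition asserts that causation exists. Read literally, it leaves one answer for an event that the drug may have caused but cannot be shown to have caused: unrelated. A literal reading therefore errs in one direction.

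Attribution is hard in this trial. There is no concurrent control (Protocol 5.4), so no comparison arm can show an excess of events independently of the investigator's opinion. In the earlier monotherapy study at this dose, 71% of patients had Grade 4 neutrophil decreases judged related, and 11% had related febrile neutropenia (Protocol 3.2.1). A serious infection in a patient with progressing lung cancer can plausibly be put down to either the disease or the drug. Events of that kind are the ones that a standard of established causation would exclude.

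What is at stake is the completeness and consistency of late and expedited safety reporting, and of the tables restricted to related events. The primary endpoint, the decision rules and the sample size are not affected.

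**Working it through.** No arithmetic applies. The check is to set the definition beside every rule that uses relatedness, and then to ask what remains when an event is judged unrelated.

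**Step 1: is there another definition?** Appendix 1 of the protocol defines AE and TEAE and notes that neither requires a causal link. It does not define relatedness. SAP 5.13.2 uses *possibly related* without defining it. The sentence in Protocol 9.2 is therefore the only definition in either document.

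**Step 2: which term does each rule use?**

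- Related, with no qualifier: Table JTJH.2.3 (after Visit 801) and 9.2.2 (SUSARs). These rules have no wording of their own to soften the definition.
- Reasonably possibly related: 9.2.1, for SAEs before first dose and after discharge. This is close to the defined phrase.
- Possibly related: 9.2.1, for progression, and SAP 5.13.2. In everyday English this is a possibility standard, which contradicts the definition.

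Three terms are thus in use, with one definition that matches the plain meaning of none of the qualified ones.

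**Step 3: what survives a judgement of unrelated?**

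- Protocol 9.2.1 has every AE after consent entered on the CRF, and Table JTJH.2.3 restricts collection by relatedness only after Visit 801.
- SAP 5.13.2 plans summaries of all TEAEs, overall and by maximum grade, whatever the attribution. It also provides, without a relatedness condition, for AEs, deaths and SAEs to be listed and summarized.
- SAP 5.13.3 lists every recorded death separately.
- Protocol 10.3.1 counts death from any cause in overall survival, and Table JTJH.2.3 continues survival follow-up about every 60 days.

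**Step 4: two illustrative cases.** Take a fatal pneumonia 20 days after the last dose, with recent neutropenia. It falls before Visit 801, which is set at 30 ± 5 days. It is recorded and enters the all-TEAE tables and the death listing under either reading. What turns on the definition is its place in the related-TEAE table, its SUSAR status if unlisted, and its SAE report if the investigator attributes it to progression. Now take a serious infection 60 days after the last dose. Under Table JTJH.2.3 it is reported only if it is treatment-related, so a literal reading of 9.2 removes the requirement to report it. If the patient dies, the death is still captured.

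**The case against.** The best defence is that the sentence is careless drafting and that investigators will follow the ordinary meaning of *possibly related*, which most of the rules print. Section 9.2 also asks for potential relatedness and tells investigators to alert the sponsor to anything unusual, whatever its cause. Neither document shows how sites apply the wording. This stands as a limit: the contradiction is in the text, but a bias in practice is not demonstrated. It does not cure the defect, because the loose terms are undefined, the one definition is strict, and two of the rules carry no qualifier.

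A reader might infer several stronger points that the documents do not support:

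- **That the related post-treatment deaths line is the only firm death summary.** It is not. SAP 5.13.2 commits to summarizing deaths without an attribution condition, although the further all-patient summary in SAP 5.13.3 is optional.
- **That nothing is collected on late events.** Deaths are followed, listed and analyzed. What is not required is an SAE report for a late event judged unrelated.
- **That the problem can be sized from expected deaths soon after stopping drug,** for example from the untreated survival of 2 to 4 months in Protocol 3.1. Such a count would fall mostly in the window where AEs are collected whatever their attribution. It would also say nothing about the share misclassified.

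**Conclusion.** The definition in Protocol 9.2 is wrong for the question that it serves and inconsistent with the terms used in 9.2.1 and SAP 5.13.2. Applied literally, it would under-classify plausible drug events. That could reduce reporting of serious events after Visit 801, of SAEs before first dose and after discharge, and of SAEs attributed to progression. It could also reduce SUSAR identification and the counts in the related-TEAE tables and the related post-treatment deaths line. Different readings could also make reporting uneven between sites.

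The number of events affected cannot be estimated from the documents. The conclusion rests on one assumption: that at least some investigators follow the printed definition rather than the everyday meaning. Total TEAE counts up to Visit 801, the death listing and overall survival are unaffected under either reading. The correction is worth making because the rules concern safety reporting and the change is small.

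**What to change.** Replace the sentence in Protocol 9.2 with one to this effect: *a reasonable possibility means that a cause and effect relationship may exist, that is, there are facts or arguments to suggest it.* Then use that one term in Table JTJH.2.3, in 9.2.1 (before first dose, after discharge and progression), in 9.2.2, and in the related-event and post-treatment death lines of SAP 5.13.2.

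The cost is one protocol sentence and conforming edits, with no new data collection. The small downside is that the reported related-event rate may be slightly higher. The change is best made before attributions accumulate, because judgements made under an ambiguous definition are hard to repair later.

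A fixed table of all deaths within 30 days of the last dose, whatever the cause, would be a reasonable addition to the SAP. It is a reporting preference and is not needed to correct this error.

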9.2.1. Serious Adverse Events

An SAE is any AE from this study that results in one of the following outcomes:

- death
- initial or prolonged inpatient hospitalization
- a life-threatening experience (that is, immediate risk of dying)
- persistent or significant disability/incapacity

- congenital anomaly/birth defect
- considered significant by the investigator for any other reason: important medical events that may not result in death, be life-threatening, or require hospitalization may be considered serious, based upon appropriate medical judgment.

Although all AEs after signing the ICF are recorded in the CRF/electronic data entry/designated data transmission methods, SAE reporting begins after the patient has signed the ICF and has received LY2606368. However, if an SAE occurs after signing the ICF, but prior to receiving LY2606368, it needs to be reported ONLY if it is considered reasonably possibly related to study procedure.

Study site personnel must notify Lilly or its designee of any SAE within 24 hours of investigator awareness of the event via a Lilly-approved method. If alerts are issued via telephone, they are to be immediately followed with official notification on study-specific SAE forms. This 24-hour notification requirement refers to the initial SAE information and all follow-up SAE information.

Pregnancy (during maternal or paternal exposure to LY2606368) does not meet the definition of an AE but should be reported. However, to fulfill regulatory requirements, any pregnancy should be reported following the SAE process to collect data on the outcome for both mother and fetus.

Investigators are not obligated to actively seek AEs or SAEs in patients once they have discontinued and/or completed the study (the patient summary CRF has been completed). However, if the investigator learns of any SAE, including a death, at any time after a patient has been discharged from the study, and he/she considers the event reasonably possibly related to the study treatment or study participation, the investigator must promptly notify Lilly.

Planned hospitalizations or procedures for preexisting conditions that were recorded in the patient's medical history at the time of enrollment should not be considered SAEs. Hospitalization or prolongation of hospitalization without a precipitating clinical AE (for example, for the administration of study treatment or other protocol-required procedure) should not be considered an SAE.

Serious adverse events, including death, caused by disease progression should not be reported unless the investigator deems them to be possibly related to LY2606368.

